## 11. Study population

### 11.1. Study setting

Patients will be enrolled from medical ICUs affiliated with Columbia University Medical Center. These ICUs include but are not limited to the following locations, all of which are in the general vicinity of Columbia University’s medical campus:

ICU short designation	Full name	Hospital building, floor location	Street address
MICU-A	Medical ICU-A	Milstein, 4 th floor	[name]
MICU-B	Medical ICU-B	Milstein, 4 th floor	[name]
NICU	Neurological ICU	Milstein, 8 th floor	[name]
AICU	Allen ICU	Allen Pavilion, 2 nd floor	[name]

The study will enroll 90 consecutive adult ICU patients who meet criteria for sepsis, are receiving appropriate antibiotics, and can complete a bedside assessment within 4 hours of ICU admission and receive the trial intervention within 6 hours of ICU admission. A replacement strategy will be used. If subjects are randomized but fail to receive the intervention or complete the Day 3 assessment, an additional subject will be enrolled to take their place with a final target enrollment of 30:30:30 patients who complete a minimum of 3 days of assessments. Specific inclusion and exclusion criteria are as follows:

### 11.2. Inclusion criteria

- Medical ICU. Subjects will be newly admitted to one of two CUMC medical ICUs during the study enrollment period;
- Age. Subjects will be eighteen or more years old at the time of ICU admission;
- Sepsis. Subjects will meet criteria for sepsis with life-threatening organ dysfunction caused by infection (Sepsis-3 third international consensus definition, 2016). According to this definition, life-threatening organ dysfunction is operationalized as an increase in the Sequential [Sepsis-Related] Organ Failure Assessment (SOFA) score of  $\geq 2$  points above baseline. Sepsis-3 criteria also require patients to have a known or suspected infection, defined as sampling of blood or any other body fluid for infection with concurrent administration of appropriate antibiotics (see Table 4);
- Appropriate antibiotics. Subjects will receive appropriate antibiotics, which will be operationalized as (1) among subjects with positive culture data, the antibiotics within classes where the organism is susceptible based on standard Clinical and Laboratory Standards Institute (CLSI) cut-offs; or (2) among subjects receiving empiric antibiotics (i.e., with negative cultures), antibiotics within classes with significant anaerobic activity. This will include  $\beta$ -lactam/ $\beta$ -lactamase inhibitor combination antibiotics, cephalosporins (generation 2 or greater), fluoroquinolones, lincosamides (clindamycin), metronidazole, and monobactams (a.g., meropenem). Vancomycin monotherapy is intentionally excluded. Antibiotics must be received within 24 hours before ICU admission or be actively ordered at the time of bedside screening;

- **Prompt intervention.** Subjects will complete study enrollment within 4 hours of ICU admission so that the intervention can be administered within 6 hours of ICU admission. The first set of recorded ICU vital signs will define the time of ICU admission.

### 11.3. Exclusion criteria

- **Inability to receive oral or enteric fluids.** Patients will be excluded if they are *nil per os* or are unable to take fluid by mouth or delivered via enteric nasal or oral tube because they would be unable to receive the study intervention;
- **Inulin allergy.** Patients will be excluded for safety reasons if they have a known chicory allergy. Serious chicory allergies are exceedingly rare although mild respiratory symptoms and IgE-mediated food allergies have been reported;
- **Hyponatremia.** Patients will be excluded for hyponatremia with serum sodium  $\leq 128$  mEq/L because the intervention will be delivered in 500 ml of free water daily. If subjects develop hyponatremia (serum sodium serum sodium 125-128 mEq/L) after enrollment and randomization which persists at the time the subject is due to receive the study intervention, the study team will confer with the treating ICU team regarding whether the intervention should be deferred or further concentrated in order to minimize free water. If subjects develop severe hyponatremia (serum sodium serum sodium  $\leq 124$  mEq/L) after enrollment and randomization, the intervention will be withheld until 2 consecutive serum sodium values are within normal limits;
- **Immunosuppression.** Patients will be excluded if they have immunosuppression, as CD4 count  $< 200$  or absolute neutrophil count  $< 500$  or reasonable expectation of either during the study intervention period. We believe that the inulin works by modifying the gut bacteria. Excluding patients who lack the ability to mount an immune response improves trial homogeneity;
- **Surgery involving the intestinal lumen.** Patients will be excluded for surgeries involving the intestinal lumen within 30 days. The most common side effects from inulin are subjective bloating and abdominal distension. Although this bloating appears to be mild and self-limited, patients with recent bowel surgeries may be at greatest risk for such symptoms and will therefore be excluded;
- **DNR or DNI status.** Such patients have limited treatment goals and will be excluded to minimize heterogeneity;
- **No LAR.** Patients will be excluded if they lack capacity for consent and have no appropriate Legally Authorized Representative (LAR) to act as surrogate decision-maker.

### 12. Enrollment strategy

Patients will be identified at the time of ICU bed allocation and screened for inclusion/exclusion criteria. After consultation with the treating ICU team, subjects who meet screening criteria will have the eligibility evaluation completed at the ICU bedside. This will be done after first obtaining agreement from the medical ICU attending of record that the patient/surrogate can be approached for the study. We anticipate that  $>50\%$  of patients will lack decision-making capacity and will accept consent from a surrogate in these situations, as previously described by our group. Issues related to altered capacity, privacy and time for decision-making, consent of LARs, and ongoing consent are discussed in detail in the **Human Subjects and Recruitment and Safety**

**Procedures** section. We expect that patients will usually be initially enrolled with surrogate consent. Patients who are on study will then be reassessed for capacity at each interaction, with the final determination of capacity made by the treating ICU team. When subjects regain capacity, they will make their own determination of whether or not to continue in the study. If subjects do not regain capacity by the time of hospital discharge, surrogate consent will be accepted as final. This approach, which we have used before, preserves complete patient autonomy while recognizing that the target population for the study is unlikely to have decision-making capacity at the time of ICU admission.

#### Compliance statement regarding consent

This research will meet the requirements of **10 U.S. Code 980** for experimental human subjects research that “(1) the informed consent of the subject is obtained in advance; or (2) in the case of research intended to be beneficial to the subject, the informed consent may be obtained from a legal representative of the subject.”

#### Retention

Potential loss of patients after randomization will be from death/discharge prior to ICU Day 3, or withdrawal of consent (e.g., after initial surrogate consent). In our ongoing ICU cohort studies, there has been 11.3% mortality within 3 days and a 0% Day 3 discharge rate. Additional patients will be enrolled for patients who do not complete the Day 3 assessment due to death or discharge. Thus, we expect to enroll 102 patients to obtain 90 who are able to donate a Day 3 sample and therefore can included in the intent-to-treat analysis.

### **12.1. Randomization and blinding**

Randomization and data entry will take place through a secure, web-based system managed by the CUMC Data Coordinating Center (DCC) headed by [name]. This password-protected system is based on the Research Electronic Data Capture (REDCap) platform. The Research Nurse will use paper clinical research forms (CRFs) to document the initial screening process. When this information is entered into REDCap, the system will automatically generate a subject identifier and randomization code using 1:1:1 randomization in randomly permuted blocks of 6. This randomization code will be electronically communicated to the research pharmacy along with a separate key which will allow them to identify the random assignment. The Columbia Research Pharmacy will prepare the study intervention in indistinguishable semi-opaque fluid bags. Although inulin is readily soluble at the study doses, the opacity of these bags will eliminate any possibility that a small amount of precipitant might reveal the study assignment to the ICU nurses who deliver the intervention. Five drops of non-caloric flavoring syrup (McKesson Supply, Yonkers, NY, Product #570727) will be placed into the reconstituted inulin/placebo to prevent any possibility of accidental unblinding based on taste in patients who are alert. The patient, treating ICU team including the ICU nurse, and study team will remain blinded to each assignment until the completion of the trial, with the DCC preparing unblinded safety reports for the DSMO at pre-specified intervals.

#### 12.1.1. Clinical need for unblinding

It seems unlikely that clinical need for unblinding will arise. If this occurs, the PI will coordinate with the DCC to facilitate unblinding for the treating ICU team. In any case of unblinding, data collection and follow-up will be maintained and the patient analyzed per-protocol.

### **12.2. Delivery of the intervention**

The treating medical team will order the study intervention as a non-formulary medication to be delivered by ICU nurses, as they would any other medication, and the study team will work to ensure prompt delivery of the intervention with a goal of having it delivered within 24 hours from

the first set of ICU vital signs. Delivery of the intervention will be managed by ICU nurses who are not part of the study team by encouraging the subject to drink the liquid formulation or, in subjects who are not taking oral medications, by attaching the intervention to the patient's oral or nasogastric tube. The time of dosing will be recorded electronically within the patient EMR and documented by study staff on the CRFs and within REDCap.

### 12.3. Premature cessation of the intervention

Efforts will be made to ensure that all subjects who are randomized receive the study intervention. The initial medication order will specify that the study intervention is to be given q12h for a total of 14 doses. The study intervention will be stopped under the following conditions:

- Death;
- Discharge from the hospital;
- Request to withdraw from the study by the patient or surrogate. This request can be made at any time, without providing a reason. Consent to continue data collection and retain samples already collected will be sought in these situations;
- Definite clinical indication or contraindication becomes apparent. If the treating ICU team feels at any time that the patient needs or should not have fiber supplementation, the intervention will be immediately halted. The patients will remain in the study for follow-up and the intervention will be held as long as the indication/contraindication remains. In general, if the indication/contraindication resolves within the 7 day timeframe of the intervention, the intervention will be resumed. If the intervention is withheld for hyponatremia, the intervention will be resumed only once 2 consecutive serum sodium values are within normal limits;
- Adverse or serious adverse event related to the study intervention. Such events will constitute unanticipated problems. The patient will remain in the study for follow-up, but no further interventions will be administered.

## 13. Study assessments

The total study duration will be no more than 30 days of bedside assessments and no more than 6 months of telephone follow-up, both measured from the first recorded set of ICU vital signs. Samples will be gathered and bedside assessments made at the following intervals after ICU admission or until hospital discharge/death: baseline, 3 days, 7 days, 14 days, and 30 days. During study assessments, data will be combined from the following sources: (1) samples collected by the study team, (2) bedside assessments, and (3) data from the EMR.

### 13.1 Sample collection and storage

Sample collection is focused around **rectal swabs** because the timing of swabs (as opposed to whole stools) can be precisely dictated and because rectal colonization with MDR bacteria best reflects overall MDR colonization status and risk for subsequent infection. Samples are described below.

- **Rectal swabs.** At each study assessment, deep flocked nylon swabs of the rectum will be performed in duplicate to allow independent processing of swabs for 16S rRNA gene sequencing/multiplex qPCR and for bacterial culture of MDROs. Swabs will be inserted 5 cm rectally with patients in the left lateral decubitus position and rotated 5 times, with adequate

sampling verified by looking for fecal staining. Swabs to be sequenced will be flash-frozen at -80°C for long-term cold storage and batched extraction; swabs to be cultured will be transported on soy broth with 20% glycerol (Becton Dickinson, Franklin Lakes, NJ) for culture or, when culture cannot be performed immediately, for storage overnight at 4° C and culture the following morning.

- **Whole stools.** Nursing staff will collect the first spontaneous whole stool subsequent to each study assessment. 4 x 8 ml aliquots of stool will be flash-frozen and stored at -80 ° C.
- **Oral swabs.** Two cotton-tipped oral swabs will be used to gather a composite of the oral flora by brushing the following consecutive locations x 10 each: left cheek, right cheek, hard palate, tongue, floor of the mouth, and maxillary gingivae (same as the Human Microbiome Project). Swabs will be flash frozen at -80 ° C.
- **Urine.** ICU nurses will withdraw 2 x 8 ml of urine using standard technique from the urinary catheter sampling port. In patients who lack a urinary catheter, clean catch urine samples will be accepted and aliquoted as above.
- **Blood.** Residual blood from clinical samples drawn immediately prior to each study assessment will be retrieved by the study team. For each subject, one 6 mL serum-separator and one 8 mL EDTA tube will be retrieved. Buffy coat will be separated by centrifuge and with 1-2 mL aliquots generated for plasma/buffy coat and stored at -80 ° C. This strategy spares subjects the need for an additional blood draw.

Oral swabs, urine, and blood will be stored for future testing. The rationale for collecting these additional samples is that they are non-invasive, can be easily collected, and will provide opportunities for future studies seeking to explore additional markers or mechanisms (e.g., urinary 3-indoxyl sulfate for gut microbiome disruption or micro-RNAs in sepsis). All sample storage will be in the PI's -80°C freezer unit (P&S-8) except for the fresh rectal swab used for culture which will be stored within the [name] lab (P&S-9). Assays performed from rectal swabs and whole stools (SCFAs) are described below.

### 13.2. Sample assays

The assays described below will be performed from rectal swabs or whole stools (for fecal SCFA levels). Residual sample material will be retained in -80°C storage for the duration of the study.

- **16S rRNA gene sequencing.** 16S rRNA gene sequencing will be performed to determine the **primary outcome**. From extracted rectal swab DNA, polymerase chain reaction (PCR) will be performed on a Bio-Rad T100 Thermal Cycler (Bio-Rad, Hercules, CA) to amplify the V4 hypervariable region of the 16S ribosomal RNA gene with primers derived from Klindworth *et al.* appended with overhang sequences for compatibility with Illumina index and sequencing adapters (Illumina, San Diego, CA). Samples will be purified with Agencourt AMPure XP beads (Beckman Coulter, Jersey City, NY) and quantified using the Quant-iT broad range dsDNA Assay Kit (Thermo Fisher Scientific, Fair Lawn, NJ). Libraries will be normalized, pooled, and denatured in preparation for cluster generation and sequencing, which will be performed on the Illumina MiSeq 300PE.
- **Bacterial culture.** Aerobic culture will be performed to determine the **secondary outcome**. Culture has been selected for the primary outcome because culture identifies viable bacteria, remains the most common clinical method for testing for MDRO colonization in

the ICU, and best predicts longterm risk for organism-specific infection. Additional analyses will utilize alternative methods for classifying MDROs. Cultures will identify MRSA, VRE, and MDR Gram negatives, which cause 94% of all MDR bacterial infections in the ICU. Rectal swabs will be gently vortexed to dissociate DNA from the swabs into the broth media. Media will then be split into equal aliquots and plated under a laminar flow hood for MRSA (Spectra-MRSA, Remel), VRE (Spectra-VRE, Remel), and ESBL or *Klebsiella pneumoniae* carbapenemase (KPC)-producing bacteria ([name] lab). In addition, we will plate cultures on Gram-negative selective agar (MacConkey II agar, Becton Dickinson) directly and at three serial dilutions for semi-quantitation ( $10^{-2}$ ,  $10^{-4}$ , and  $10^{-6}$ ). While the main analysis will be based on a categorical classification of MDROs (present vs absent), an exploratory analysis will be conducted using semi-quantitative culture data. Preliminary data show that these dilutions will yield a countable number of colonies. After 18-24 hours of aerobic growth, selective plates will be classified as positive vs negative for growth according to the media characteristics. The colony-forming units (CFUs) on the non-selective plates for Gram positives/negatives will be counted to provide relative quantification of each MDRO based on the total CFU counts from the non-selective plates. If multiple non-selective plates show growth, the plate with 10-100 colonies will be used for CFU counting with results normalized to the  $10^{-2}$  plate. From these plates, organisms will be identified using the VITEK 2 system (bioMerieux) and AST-N010/020 cards with confirmatory testing as needed. Resistant isolates will be stored for whole genome sequencing analyses.

- **Quantitative PCR.** Quantitative PCR for resistance genes will be performed as an additional outcome. DNA will be extracted from rectal swabs (MoBio PowerFecal, Carlsbad, CA) and assessed using multiplex quantitative PCR (Qiagen Cat. No. 330261, Valencia, CA) for 87 common antibiotic resistance genes. In this assay, 250 ng of template genomic DNA will be added to each reaction on a 96-well plate which will be run on a StepOnePlus RT-PCR machine using the following cycling conditions: initial denaturation for 10 min at 95° C, cycling 45 x 15 sec at 95° C denaturing followed by 2 min at 60° C annealing and extension. Controls will detect the presence of bacterial DNA, PCR inhibitors and background (no template control (NTC)). PCR cycle thresholds ( $C_T$ ) of <35 will be considered positive for the presence of any given gene. Adequate reactions will be determined by  $C_T$  values of <29 for pan-bacterial reference genes (e.g., *16S rRNA*, *gyrA*, *recA*, *rpoB*) and positive PCR controls (PPC)  $C_T$  values of <24. Linearity and sensitivity for this PCR have been determined using synthetic templates over a 6-log serial dilution ranging from 1 to 1 million copies, with results verified across multiple antibiotic resistance genes using pyrosequencing.
- **Fecal SCFA levels.** Fecal SCFAs levels will be assayed as an additional outcome. Whole stools will be aliquoted and diluted with 80% ethanol to be agitated at 4°C. After centrifugation, 20 µl of supernatant from the homogenized samples will be mixed with 20 µl of 200 mM N-(3-Dimethylaminopropyl)-N'-ethylcarbodiimide hydrochloride (1-EDC HCl) in 5% pyridine and 40 µl of 100 mM 2-Nitrophenylhydrazine (2-NPH) in 80% acetonitrile (ACN) with 50 mM HCl. After a brief incubation, ACN will be added to the solution which will be injected onto a 6490 triple quadrupole mass spectrometer (Agilent, Santa Clara, CA) and tested for concentrations of the SCFAs butyrate, acetate, and propionate.

### 13.3. Bedside assessments including data gathered from the EMR

During each study assessment, a study-specific Case Report Form (CRF) will be used to record the following data: origin for admission (classified as from the hospital floor, operating room, emergency room, or outside ICU transfer based on the most recent location prior to CUMC ICU

admission); the Glasgow Coma Scale (GCS); the use of life support (classified as present vs absent) including the use of mechanical ventilation, hemodialysis, or additional life-support devices such as extra-corporeal membrane oxygen (ECMO) or an intra-atrial balloon pump (IABP); and the presence or absence of intravenous lines or catheters including a central venous catheter, urinary catheter, arterial catheter, nasal or oral gastric tube, or rectal tube. Using duplicate data entry, anonymized CRF data will be transferred into the secure REDCap database. Additional clinical variables will be entered directly into REDCap from the EMR. These variables will include laboratory analyses, all of the component variables of the Sequential Organ Failure Assessment (SOFA) score, measures related to nutritional intake, and ICU interventions including administration of vasopressors, proton pump inhibitors, and antibiotics (with the name of the antibiotic and route of administration recorded).

### 13.3.1. Tolerability

Patients who are alert will be asked regarding abdominal bloating which will be graded on a 4-point Likert scale (0=none, 1=a little, 2=a moderate amount, 3=a lot/severe). When patients are not alert, this will be graded as “unable.” ICU nurses will be asked to grade the average consistency of stools within each preceding 24 hours on a 5-point scale (0=like water, 1=like porridge, 2=loose but with chunks, 3=formed, soft, 4=formed, hard). This information will also be recorded from the EMR into REDCap as a separate entry. When subjects have no stools within the preceding 24 hours, this will be recorded as “no stools.” The frequency of stools within the preceding 24 hours will be recorded as an integer at each study assessment. Again, this will be done based both on the nurse’s in-person report and separately based on EMR documentation.

ICU nurses will be additionally asked regarding the presence or absence of the following symptoms during the 24 hour period prior to each study assessment: nausea, vomiting, bowel obstruction, and abdominal pain. This data will be recorded categorically on the CRFs/REDCap and will appear on DSMO reports.

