### 6.3. Inulin in the ambulatory setting

Inulin has been studied in over 400 ambulatory patients where it has shown excellent safety and tolerability. No serious adverse events have been reported in trials using doses up to 34 g/day inulin or 55 g/day mixed fiber, with self-resolving bloating the main side effect. Three trials specifically examined outcomes related to the ability of inulin to prevent colonization or infection. First, Dewulf *et al.* randomized 30 patients to inulin 16 g/day vs placebo; the inulin group had a doubling of *F. prausnitzii* and other SCFA-producers and concurrent decreases in serum CRP and LPS concentration. Second, Lecerf *et al.* randomized 60 volunteers 1:1:1 to placebo, a combination xylo-oligosaccharide (XOS), or inulin-XOS. The inulin group had the highest post-treatment SCFA levels and butyrate levels, the lowest circulating LPS, and decreased gene expression for the pro-inflammatory cytokines IL-1 $\beta$ , TNF $\alpha$ , and IL-12. Third, Miguez *et al.* found that an inulin-like fructo-oligosaccharides (FOS) preserved gut microbiome diversity after broad-spectrum antibiotics, mitigated loss of SCFA producers, and increased butyrate levels 3-fold. **Table 1** lists selected studies of inulin in the ambulatory setting, focusing on those with results most relevant to this project.

[figure not shown]

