### 10.3. Additional outcomes:

10.3.1. *Feasibility.* Descriptive demographic and clinical data will be compared across study groups to assess adequacy of randomization. Summary statistics (count data) will be recorded for patients across all 3 intervention arms to assess feasibility as (1) the enrollment rate (enrolled)/(enrolled+refusals) over each 12 month period; (2) protocol adherence (proportion of randomized subjects who receive 1 or more doses of the allocated intervention); and (3) fidelity of the intervention (defined as the proportion of high/low inulin allocated vs received and also categorically as receipt of 90% or more allocated doses of inulin across groups). Feasibility goals are as stated in Aim 1.

10.3.2. *Rates of pre-specified AEs.* There will be active ascertainment of AEs in the following categories, which will be compared between intervention groups. This will be done through the end of the intervention period (ICU Day 7) and also through Day 30/discharge to assess for delayed AEs.

- Stool frequency, measured by subject or nursing report by the number of spontaneous stools over the 24 hours preceding each assessment;
- Stool consistency, measured by subject or nursing report as an ordinal variable (0-4) over the 24 hours preceding each assessment;

- Abdominal bloating, measured by subject or nursing report as an ordinal variable (0-3) over the 24 hours preceding each assessment.
- Electrolyte abnormalities, measured by examining for differences in median values, minimum/maximum values, and proportions of values outside the normal range. This will be done for glucose, calcium, magnesium, phosphate, potassium, and sodium.
- Nausea, vomiting, obstruction, and abdominal pain. These will be recorded as present or absent based on bedside assessment of the subject or based on the nursing impression.
- Culture-proven infections, which will be considered both an AE and an outcome (see 10.3.4).

10.3.3. *Antibiotic resistance gene fraction on ICU Day 3.* DNA will be extracted from rectal swabs (MoBio PowerFecal, Carlsbad, CA) and assessed using multiplex quantitative PCR (Qiagen Cat. No. 330261, Valencia, CA) for 87 common antibiotic resistance genes. Within-individual differences in multiplex qPCR results will be compared from baseline to Day 3 both as summed changes and within relevant gene categories (e.g.,  $\beta$ -lactamase resistance genes) and compared between intervention groups.

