#### **15. Safety and adverse events (AEs)**

Adverse health events, laboratory irregularities, and even death are expected in ICU patients with sepsis and it would be difficult or impossible to accurately document and label all adverse health events. This is a common problem faced by ICU trials. The solution recommended by academic critical care research groups (e.g., Cook *et al.*) is to pre-specify AEs of interest for careful monitoring. In keeping with this approach, this study will produce detailed reports of these AEs for the DSMC at standard intervals while only unanticipated problems that also meet criteria for serious adverse events (SAEs) will be reported to the DSMC in real time. AEs will be reported for all individuals who have received one or more doses of the intervention. This study has pre-specified AEs in the following categories.

- Bloating: graded 0-3 based on patient report: patient mean and maximum values will be reported;
- Stool consistency and frequency: graded 0-4 for consistency and with an integer denoting frequency over 24 hours based on nursing report. For each patient, mean and maximum values will be reported;
- Electrolyte imbalances: For each patient, the minimum and maximum values for serum calcium, magnesium, phosphate, potassium, and sodium will be reported. This will be done for the 7 days of the intervention period and separately from Day 7 through Day 30/discharge;
- Gastrointestinal AEs: the gastrointestinal AEs of nausea, vomiting, bowel obstruction, and abdominal pain will be recorded as present or absent for each assessment and separated from other AEs to improve early pattern recognition by the DSMO;
- Infections: Infections are both an AE and an outcome and will be adjudicated as previously described. For each infection, the date of the infection, suspected site, organism, and antibiotics received will be recorded. Infections will be further classified as MDR vs non-MDR using the criteria previously described;
- Death: death will be gathered from the hospital EMR, which interfaces with the social security death index.

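### Three sections disagree on who scores bloating, and under two of them it goes unscored at any visit where the patient is not alert

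*Combined protocol and SAP*

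**What the plan says.** The bloating measure is defined in three places.

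- Section 10.3.2 (under Additional outcomes): "Abdominal bloating, measured by subject or nursing report as an ordinal variable (0-3) over the 24 hours preceding each assessment". It is to be compared between arms through ICU Day 7 and again through Day 30 or discharge.
- Section 13.3.1 (Tolerability): "Patients who are alert will be asked regarding abdominal bloating which will be graded on a 4-point Likert scale". For everyone else, "When patients are not alert, this will be graded as" 'unable'. In the same section nurses are asked about stool consistency and frequency, nausea, vomiting, bowel obstruction and abdominal pain, but not about bloating.
- Section 15 (Safety and adverse events): "Bloating: graded 0-3 based on patient report: patient mean and maximum values will be reported". Adverse events are reported for everyone who received at least one dose.

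On the importance of the symptom, section 6.3 summarises the ambulatory trials "with self-resolving bloating the main side effect", and section 11.3 says: "The most common side effects from inulin are subjective bloating and abdominal distension". On the state of the patients, section 12 expects that more than 50% "of patients will lack decision-making capacity and will accept consent from a surrogate". It adds that capacity is checked again at every contact.

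**The concern.** A case report form built from 13.3.1 cannot deliver the measure that 10.3.2 promises. Section 15 sides with 13.3.1, so no later text restores the nurse's report. The scores that go missing are not a random subset: they are missing because the patient is not alert, which in a sepsis population is likely to follow sedation and severity.

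Section 5.2 gives feasibility and safety as the purpose of the trial. What is at stake is whether the bloating figures sent to the safety committee, and the comparison by dose, describe all treated patients or mainly those well enough to answer. A visit left ungraded cannot be turned into a 0-3 score afterwards.

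**Working it through.** The plan gives no expected bloating rate, no share of patients not alert, and no power statement for this item, so there is no stated figure to reproduce. The check is a comparison of texts, followed by an illustration of size.

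**1. The three definitions side by side**

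| Section | Who supplies the grade | If the patient is not alert | Summary |
|---|---|---|---|
| 10.3.2 | Subject or nurse | Nurse can grade 0-3 | Compared between arms |
| 13.3.1 | Alert patient | 'Unable', no grade | None stated |
| 15 | Patient | Not addressed | Patient mean and maximum |

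The first row conflicts with the other two. No section says whether an 'unable' visit is dropped, carried or counted when the mean, the maximum or the arm comparison is formed.

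**2. Bloating is the exception among the gastrointestinal items**

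Section 10.3.2 accepts the nurse's impression for nausea and abdominal pain, which are also subjective, and 13.3.1 collects both from nurses. Section 6.1 judged fiber intolerance in the sponsor's own ICU cohort partly from charted abdominal distension, and section 9.2.2 cites that cohort's tolerance in its dose rationale. An observer's record of distension is therefore something this site has used before.

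**3. Which visits count during treatment**

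Section 13 schedules assessments at baseline and Days 3, 7, 14 and 30, until discharge or death. Each bloating grade covers the previous 24 hours (10.3.2), and dosing lasts 7 days. Only Days 3 and 7 can yield a post-baseline grade within the intervention period. A patient not alert on both days has none for that period.

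**4. Illustration at one visit**

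Inputs: 30 patients per arm completing Day 3 (section 11.1), and *s*, the share not alert at the visit, which is an assumption because the documents do not give it.

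Gradable per arm = 30 × (1 − *s*):

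- *s* = 25%: 30 × 0.75 = 22.5, about 22
- *s* = 50%: 30 × 0.50 = 15
- *s* = 70%: 30 × 0.30 = 9

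Under 10.3.2, with the nurse grading when the patient cannot, up to all 30 would have a grade.

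**5. Illustration over Days 3 and 7 together**

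One gradable visit is enough for a patient-level mean and maximum. Suppose *s* is the same on both days and all 30 patients are still in hospital on Day 7. If the same patients are not alert both times, the numbers in step 4 stand. If alertness on the two days were independent, the number with at least one grade is 30 × (1 − *s*²):

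- *s* = 25%: 30 × (1 − 0.0625) = 28.1, about 28
- *s* = 50%: 30 × (1 − 0.25) = 22.5, about 22
- *s* = 70%: 30 × (1 − 0.49) = 15.3, about 15

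Alertness probably persists to some degree, so the truth is likely to lie between the two sets.

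**The case against.** The strongest reply concerns scale. A reader might infer from section 12 that bloating will be missing in more than half of the patients. The documents do not support that. Capacity to consent is not alertness: a confused patient may be unable to consent and still answer a four-point question. The figure is given in the setting of consent around ICU admission, section 12 allows for patients regaining capacity, and step 5 shows that a missed visit is not a missing patient. This part of the objection stands.

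A reader might also express the loss as an upper confidence limit on a zero-event rate. The plan uses no such rule for bloating: it is an ordinal score, summarised by mean and maximum and compared between arms, and some bloating is expected. That calculation would not measure what the plan loses.

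Nor is bloating the only tolerability measure. It is one of several pre-specified adverse events within an additional outcome. Stool measures, nausea, vomiting, obstruction and abdominal pain come from nurses for all patients, and feeding interruptions are recorded for those on tube feeds (13.3.2). The 'main side effect' statement in section 6.3 rests on ambulatory trials; in Table 2 only one of seven ICU trials lists bloating, and section 11.3 describes it as mild. So the gap is one symptom, not gastrointestinal tolerability as a whole.

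Finally, 'unable' is a defensible entry for a self-report item, section 11.3 lists bloating and distension as separate things, and the conflict could be removed by narrowing 10.3.2 instead. That would make the text consistent but keep the gap. Reporting nurse ratings separately fills it without mixing the two constructs.

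**Conclusion.** The inconsistency is real and unresolved in the documents. As 13.3.1 and 15 are written, bloating has no score at any visit where the patient is not alert, and the reported means, maxima and arm comparison then over-represent the more alert patients. That these are also the less ill ones is a reasonable inference, not a stated fact.

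The size is unknown. The range in the working rests on an assumed 25% to 70% not alert at a visit; the capacity figure at entry is only a proxy. Because allocation is randomised, the share ungraded should be similar across arms unless treatment affects alertness, so the expected damage is to representativeness and precision rather than a false difference between doses.

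The primary and secondary outcomes are untouched. The point is moderate, but worth settling before data collection because ungraded visits cannot be recovered and the remedy is cheap.

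**What to change.** Reconcile 13.3.1 and 15 with 10.3.2:

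1. In 13.3.1, keep the patient's own grade when the patient is alert. When the patient is not alert, record 'unable' for self-report and have the bedside nurse give a 0-3 abdominal bloating/distension grade in the interview already held at each assessment.
2. In 15, report patient-rated and nurse-rated grades separately, by arm.
3. State that 'unable' visits are left out of the patient-rated mean and maximum, and say how they are treated in the arm comparison.
4. Report the number gradable per arm and visit. The Glasgow Coma Scale is already recorded at each assessment (13.3), so the ungraded visits can be described by level of consciousness.

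The cost is one question in an existing interview, one form field and a few lines of text. The downside is that nurse ratings are less exact than self-report and partly capture distension rather than the felt symptom, which is why the two should not be pooled.
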